4.4.1 Secondary Objective #1: All-cause mortality

The secondary objective #1 is to test the hypothesis that aCRT ON reduces all-cause mortality compared to aCRT OFF. All-cause mortality is one of the two components that comprise the primary endpoint.

Hypothesis

Let $S_T(t)$ and $S_C(t)$ denote the proportion of patients in the treatment arm (aCRT ON) and control arm (aCRT OFF), respectively, that have not died up to time t . Let $h_T(t)$ and $h_C(t)$ be the associated hazard functions. Under the Cox regression model that assumes proportional hazards, $h_T(t) = HR \cdot h_C(t)$, where HR is the hazard ratio of treatment compared to control. The null and alternative hypotheses are:

$$H_0 : HR = 1$$

$$H_A : HR \neq 1$$

Analysis Method

Similar to the primary endpoint, the hypothesis regarding the aCRT effect on all-cause mortality will be tested using a Cox proportional hazards regression model with a random site effect (frailty), stratified by NYHA class at enrollment. Section 4.3.2 has described this model in details. The analysis will be conducted using code similar to:

```
PROC PHREG DATA=mortality;  
  CLASS NYHA site;  
  MODEL time*death(0) = rand / TIES=efron;  
  STRATA NYHA;  
  RANDOM site/dist = gamma;  
RUN;
```

In these codes, death = 1 given an adjudicated death and death = 0 otherwise; time to death starts from the date of randomization and ends at the date of death for those who die, or the date of last documented follow-up since randomization for those who are censored. Date of last documented follow-up since randomization is the maximum value among the dates of randomization, randomization programming, any study scheduled follow-up visit, exit, adverse event onset, adverse event resolved, system modification, and healthcare utilization.

The model assumptions will be checked using the same methods that are described in detail in section 4.3.2 for the primary endpoint. That is, the assumption of proportional hazards between the treatment arms will be checked by testing the significance of treatment by time interaction term; and, the assumption of constant hazard ratio for treatment across NYHA classes will be checked by testing the significance of treatment by NYHA class interaction and evaluating the hazard ratio for treatment within each NYHA class.

Missing Data

Similar to the analysis for primary endpoint, we assume non-informative censoring for lost to follow up in the analysis of all-cause mortality.

Sensitivity Analyses: LBBB Determination and aCRT Programming

The first sensitivity analysis is to verify the effect of aCRT treatment on all-cause mortality among the true LBBB patients. The same model used in the primary analysis will be used in this sensitivity analysis. The only difference is that patients included in the sensitivity analysis must have their LBBB confirmed by ECG Core Lab.

```
PROC PHREG DATA=mortality_LBBB;  
  CLASS NYHA site;  
  MODEL time*death(0) = rand / TIES=efron;  
  STRATA NYHA;  
  RANDOM site/dist = gamma;  
RUN;
```

The second sensitivity analysis is to check the effect of aCRT on all-cause mortality based on the actual aCRT programming, given that patients' LBBB has been confirmed by the ECG Core Lab. Again, actual aCRT programming will be a time-varying covariate, meaning patients whose actual aCRT programming change over time will have multiple records in the input dataset. This will be performed using the COVSANDWICH option in the SAS PHREG procedure, and random site effect will not be considered in this sensitivity analysis.

```
PROC PHREG DATA=mortality_LBBBCross COVSANDWICH (AGGREGATE);  
  ID pt;  
  CLASS NYHA site pt;  
  MODEL (start,stop)*death(0) = rand / TIES=efron;  
  STRATA NYHA;  
RUN;
```

Subgroup Analysis: Interaction with Treatment

Same as for the primary endpoint, the subgroups to be considered for all-cause mortality include:

- Geography: US/Canada vs. International
- Age
- Gender: Males vs. Females
- QRS duration: ≤ 150 ms vs. > 150 ms
- AV conduction time: median as cutoff
- LBBB: Core Lab confirmed vs. Core Lab not confirmed
- NYHA class (in different model where NYHA class is a covariate not a stratification factor)
- HF etiology
- Renal dysfunction
- Diabetes

The effects of treatment by subgroup interaction on all-cause mortality will be evaluated using codes similar to:

```
PROC PHREG DATA=mortality_Subgroup;  
  CLASS NYHA site Subgroup;  
  MODEL time*death(0) = rand subgroup rand*subgroup / TIES=efron;  
  STRATA NYHA;  
  RANDOM site/dist = gamma;  
RUN;
```

Ancillary Analysis: Covariate Adjustment

The process of ancillary analysis for all-cause mortality is exactly the same as that for the primary endpoint. Refer to section 4.3.6 for details on model building and model selection. Note that NYHA class at enrollment will be regarded as a covariate not a stratification factor in this ancillary analysis. Therefore, the entire process will be based on frailty models. For example, in the beginning the effect of each subject characteristic on all-cause mortality will be tested in a univariate frailty model using codes similar to the below.

```
PROC PHREG DATA= mortality;
  CLASS site SubjCha; * CLASS only if SubjCha is categorical;
  MODEL time* death(0) = SubjCha / TIES=efron;
  RANDOM site/dist = gamma;
RUN;
```

After that, the final multivariate Cox regression model will be determined from the full model using backwards selection. Again, the backwards selection will be performed manually because the SAS PHREG procedure ignores the SELECTION option for the frailty model analysis.

Determination of Patients/Data for Analysis

Similar to the primary endpoint, the primary, subgroup and ancillary analysis for all-cause mortality will follow the ITT principle and include all randomized patients; sensitivity analyses will only include randomized patients with ECG Core Lab confirmed LBBB and ITT principle is not applicable to the sensitivity analysis per actual aCRT programming.

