1.3 Study oversight

The **Steering Committee** (SC) is responsible for the scientific content of the study and provides input for the execution. The SC will also approve requests for crossovers and will review accuracy rates of LBBB (as determined by the ECG Core Laboratory).

The **Data Monitoring Committee** (DMC) provides oversight for the overall conduct of the study, and specifically for subject safety and scientific validity. The DMC will review interim results of the study.

The **Endpoint Adjudication Committee** (EAC) will adjudicate the HF- and AF related endpoints.

The **ECG Core Laboratory** will review all baseline ECGs for presence of LBBB and normal AV conduction. Feedback on accuracy rates will be presented to the Steering Committee and to the sites.

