5.2.2 Endpoint Adjudication Committee

All potential endpoints will be reviewed by the Endpoint Adjudication Committee (EAC). Please refer to Appendix D for an overview of the EAC’s tasks.

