5.7 Minimization of Bias

Selection of subjects, treatment of subjects, and evaluation of study data are potential sources of bias. Methods incorporated in the study design to minimize potential bias include (but are not limited to):

- Patients will be evaluated at baseline to confirm eligibility for enrollment with defined inclusion/exclusion criteria prior to implant and randomization.
- An ECG Core Laboratory will be used to confirm presence of LBBB and normal AV conduction.
- Subjects will be randomized to ensure comparable treatment groups.
- Subjects will be blinded to their treatment group.
- Subject demographics will be collected at baseline and differences that may affect primary endpoints will be identified.
- To ensure a widespread distribution of data between centers, the maximum number of randomized subjects allowed per center is no more than 200.
- All implanters in the study will be experienced in the implant of CRT devices.
- Data collection requirements and study procedures will be standardized across all centers and geographies.
- All study center personnel and Medtronic personnel will be trained on their respective aspects of the study using standardized training materials. All study clinicians will be trained on and required to follow the CIP.
- Monitoring visits will be conducted for adherence to the CIP and to verify the CRF data against the source data.
- HF events and deaths will be adjudicated by an independent and blinded EAC.
- An independent DMC will review endpoint and other data to monitor the overall integrity of the study.

- The Steering Committee members will not have influence on the HF treatment decisions by center investigators during the trial, except for approval for crossover, as described in Section 5.5.
- The analysis will be intent-to-treat, following pre-defined statistical methods specified in this Clinical Investigation Plan and the Statistical Analysis Plan.
- Registration of the trial on clinicaltrials.gov and the publication plan will ensure that study results will be reported.

In summary, potential sources of bias that may be encountered in this clinical study have been considered and minimized by careful study design.

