APPENDIX D: ENDPOINT ADJUDICATION COMMITTEE (EAC)

Point	Examples
EAC will be used	Ongoing review of events contributing to the primary endpoint for this study will be provided by an independent blinded Endpoint Adjudication Committee (EAC).
Who will be involved	The EAC will have at least three members, including at least one physician specializing in electrophysiology, and at least one specializing in heart failure management. A chairperson from among those members will be identified. None of the EAC members will be participating investigators in the AdaptResponse study.
Responsibility of the EAC	
The EAC will establish standards for adjudicating HF events, using the ACC/AHA and ESC Guidelines as a basis for diagnosis and adjudication.
 
The EAC will be responsible for assessing applicable Healthcare Utilizations and events during the study, assessing the cause of hospitalizations and outpatient treatment, to determine HF relatedness for study objectives.
 
The EAC will meet at regular intervals throughout the course of the study to assess events, and determine whether these events should contribute to the primary and secondary endpoints of the AdaptResponse Study.

Recommendations	The EAC will be advisory to the sponsor and the Steering Committee. The EAC will determine events that will contribute to the primary and secondary endpoints of the study. Review and quorum adjudication by the committee is required to govern any event to the primary and/or secondary endpoint(s).
Heart Failure Relatedness definition	The category for heart failure relatedness will include worsening heart failure signs and symptoms such as hypervolemic and hypovolemic status requiring the administration, alteration, adjustment or augmentation of HF therapy (diuretics, inotropes and/or vasodilators etc.) or the utilization of certain treatment devices. Intervention for heart failure decompensation (HF event) is defined as an event requiring “invasive intervention (i.e. IV diuretics, ultrafiltration, or equivalent) or inpatient hospitalization”
Decision Boundaries	The EAC will make decisions as to the relatedness of the HF event. They will not be responsible for evaluating adverse events, deaths or the safety of the patients in the study (See DMC).

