4.3.2 Analysis Methods

The hypothesis will be tested using a Cox proportional hazards regression model with a random site effect (frailty), stratified by NYHA class at enrollment. In this combination of stratified Cox regression and frailty model, the hazard for subject i from site j with NYHA class k at enrollment is:

$$\lambda_{ijk}(t) = \lambda_{0k}(t) \xi_j \exp(\beta X_{ijk})$$

where $i = 1, \dots, n$; $j = 1, \dots, J$; $k = 1, 2, 3$.

$\lambda_{0k}(t)$ is the baseline hazard of k^{th} NYHA class. This is the part of stratified Cox regression, where the baseline hazards of NYHA class play no role in the estimation of treatment effect. That is, no between-NYHA-class comparisons of treatment effect are attempted and all information about the treatment effect comes from within NYHA class comparisons. ξ_j ($j = 1, \dots, J$) are frailties or site effects that follow a gamma distribution with mean 1 and variance θ_0 independently and identically. The variance parameter θ_0 is a measure of the heterogeneity across sites in baseline risk. As θ_0 increases, the values of ξ_j become more dispersed, inducing greater heterogeneity in the site-specific baseline hazards. This is the part of random effects or frailty model.⁷ Therefore, $\xi_j \lambda_{0k}(t)$ is the baseline hazard of k^{th} NYHA class at j^{th} site, and ξ_j is constant for $k = 1, 2, 3$ NYHA class from the same site j . X_{ijk} is the randomization assignment (ACRT ON or ACRT OFF), and $\exp(\beta)$ is the hazard ratio for treatment.

The SAS PHREG procedure will be used to conduct the survival analysis of primary endpoint using code similar to:

```
PROC PHREG DATA=primary;
  CLASS NYHA site;
  MODEL time*event(0) = rand / TIES=efron;
  STRATA NYHA;
  RANDOM site/ dist = gamma;
RUN;
```

Event = 1 when a subject experienced an event that was adjudicated as primary endpoint (intervention for HF decompensation or death). Event = 0 when a subject did not experience a primary endpoint, and therefore was censored. Time to event starts from the date of randomization and ends at the date that the event occurs for those who experience

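### The SAP codes a death without adjudication as censored, while the protocol disagrees with itself on whether deaths are adjudicated at all

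*SAP*

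**What the plan says.** In the mortality model of SAP 4.4.1, "death = 1 given an adjudicated death and death = 0 otherwise"; in that model 0 means censored. The same sentence says the time variable "ends at the date of death for those who die", with no adjudication condition. For the primary endpoint, SAP 4.3.2 states "Event = 1 when a subject experienced an event that was adjudicated as primary endpoint", and names death among those events.

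The protocol describes the EAC's role with deaths in several ways:

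- Section 5.7: "HF events and deaths will be adjudicated by an independent and blinded EAC".
- Sections 5.2.1 and 5.2.2: the EAC reviews all potential endpoints and decides whether one has been met.
- Section 1.3: the EAC "will adjudicate the HF- and AF related endpoints"; death is not named. Section 8.2.2 likewise gives it heart failure and atrial fibrillation relatedness, and Table 9 names only the investigator for classifying deaths.
- Appendix D: "They will not be responsible for evaluating adverse events, deaths or the safety of the patients in the study", followed by a pointer to the Data Monitoring Committee (DMC). The same appendix requires quorum adjudication for any event counted towards a primary or secondary endpoint.

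Deaths are collected regardless. Section 8.3.1 requires every death on a Subject Death form, and sections 6.15 and 6.15.1 require vital status at exit.

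**The concern.** All-cause mortality needs two facts: that the subject died, and when. It needs no ruling on cause. Making the event indicator depend on adjudication adds a condition that can fail for administrative reasons, and a failure turns a known death into a censored observation. That conflicts with the non-informative censoring that SAP 4.3.3 and 4.4.1 assume.

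Death is the whole of secondary objective #1 and one of the two components of the primary endpoint, so the rule reaches both. Mortality also matters at the interims: Appendix C of the protocol says the study will stop if a mortality benefit is detected early. A rule that leaves some known deaths out of that comparison, with no statement of which committee must adjudicate them, should not stand in a final plan.

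**Working it through.** **The plan's own figures.** The 1100 events reproduce. With HR 0.81818, two-sided alpha 0.05 and 90% power (SAP 4.3.8), a fixed design needs 4 × (1.960 + 1.282)² / (ln 0.81818)² = 1044 events. Numerical integration of the four-look design with O'Brien-Fleming-type alpha and beta spending gives 1103. With control hazard 0.14384 per year, 3 years' accrual and 2.25 years' follow-up, the average event probability is 0.3829, so N = 1100 / 0.3829 = 2873, against 2874 stated. Neither figure depends on how deaths are coded, and the documents give no mortality event count or mortality power.

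**How one known but unadjudicated death is coded**, for a subject with no earlier heart failure event:

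| Place | Coding |
|---|---|
| SAP 4.3.2, primary endpoint | not an event; censored |
| SAP 4.4.1, all-cause mortality | death = 0; censored |
| SAP 4.4.2, competing-risk coding | HFeventCens = 2; counted as a death |

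The same person is dead in one analysis and censored in two others. The end of follow-up in 4.4.1 is also unclear: the subject is among those who die (date of death) and among those censored (last documented follow-up).

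**How many deaths could be affected.**

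- If section 5.7 governs, only deaths whose adjudication is unfinished at a data cut. Deaths first learned of at closing vital-status checks are the likeliest at the final analysis.
- If Appendix D is read as taking deaths away from the EAC, deaths might never be adjudicated.
- No passage gives a pending proportion or a number of deaths, so the loss cannot be computed.

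**Illustration for mortality.** Assume 300 or 600 deaths, a mortality HR of 0.82, unadjusted two-sided alpha 0.05 and 10% of deaths unadjudicated; none of these comes from the documents. Power = Φ(√(D/4) × |ln 0.82| − 1.960), with |ln 0.82| = 0.1985.

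- 300 deaths: 40.5% with all counted, 37.1% with 270 counted.
- 600 deaths: 68.1% with all counted, 63.5% with 540 counted.
- Standard error: multiplied by 1/√0.90 = 1.054.
- HR: about unchanged if the loss is equal in both arms, since (1 − 0.10)/(1 − 0.10) = 1. If 10% is lost in the control arm only, the HR is multiplied by 1/0.90 = 1.11; if in the aCRT ON arm only, by 0.90.

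**Illustration for the primary endpoint.** The trial runs to a fixed count of events. If a share q of true first events were uncounted deaths, reaching 1100 counted events would need 1100/(1 − q) true ones: 1158 at an assumed q of 5%, 1222 at 10%. The cost is time, together with an endpoint weighted more towards heart failure events.

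**The case against.** The best case for the plan is that the documents, taken together, expect deaths to be adjudicated. Section 5.7 says so outright, sections 5.2.1 and 5.2.2 send every potential endpoint to the EAC, and SAP 4.3.2 lists death among the adjudicated events. The Appendix D sentence groups deaths with adverse events and safety and points to the DMC, so it may mean only that safety review of deaths belongs elsewhere. On that reading nothing is lost except deaths still in the queue.

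The queue is partly managed too. SAP 4.2 aims to have all events before the visit cutoff adjudicated, and repeats the interim primary analysis on investigator-evaluated events whatever their adjudication status. It also cites the DMC charter's warning that completing adjudication may alter results.

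Most of this stands, and it limits the size of the problem. It does not remove it. The safety-only reading of Appendix D is plausible but not stated, and sections 1.3 and 8.2.2 independently leave deaths out of the EAC's remit. The back-up analysis in SAP 4.2 covers the primary endpoint at interims; none is stated for mortality or for the final analysis. No passage says how a reported but unadjudicated death is coded at the end.

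A reader might go further and infer that the mortality model would have no events, or that primary power would fall from 90% to about 74–80% by assuming that 25–35% of first events are deaths and removing them all. The documents support neither. The first lets one clause of Appendix D override section 5.7. The second rests on a death share found nowhere in the documents, and treats the trial as stopping short when SAP 4.3.1 and 4.3.8 run it until 1100 events accrue.

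**Conclusion.** The concern holds as a defect in the coding rule, compounded by a contradiction in the protocol. As written, a known death can be censored in an all-cause mortality endpoint and left out of the primary composite, while SAP 4.4.2 counts it. Whether this touches a few deaths pending at a data cut or more depends on which protocol passage governs, and the documents do not say.

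The loss therefore has no computable size. If it is small and balanced between arms, it costs some precision in the mortality comparison and some delay in the primary. If it is unbalanced, it biases the mortality hazard ratio, by about 10% in either direction for a 10% loss in one arm only. The illustrative figures depend on assumed numbers of deaths, an assumed mortality HR and an assumed unadjudicated share. The inconsistency in the wording depends on none of them.

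**What to change.** - In SAP 4.3.2 and 4.4.1, set the event indicator to 1 for every documented death after randomization, from the Subject Death form or exit vital status, whatever its adjudication status or cause. This matches SAP 4.4.2.
- In SAP 4.4.1, end follow-up at the date of death for all such subjects.
- Keep the adjudication requirement for heart failure events.
- Reconcile protocol sections 1.3 and 5.7 with Appendix D, so that they agree on what, if anything, the EAC decides about deaths. If Appendix D means only that safety review of deaths belongs to the DMC, say so there.

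The cost is a SAP wording change and a protocol clarification. The data are already collected, and no stated sample-size figure changes.

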4.3.1 Hypothesis

The null hypothesis is that the hazard ratio for treatment (aCRT ON) versus control (aCRT OFF) is equal to 1. It will be tested against the alternative hypothesis that the hazard ratio is unequal to 1.

Let $S_T(t)$ and $S_C(t)$ denote the proportion of patients in the treatment arm and control arm, respectively, that have not experienced a primary endpoint up to time t . Let $h_T(t)$ and $h_C(t)$ be the associated hazard functions. Under the proportional hazards model, $h_T(t) = HR \cdot h_C(t)$, where HR is the hazard ratio of treatment compared to control. The null and alternative hypotheses can be expressed as:

$$H_0 : HR = 1$$

$$H_A : HR \neq 1$$

Endpoint Definition

The primary endpoint is the composite of all-cause death and any intervention for heart failure decompensation (HF event) as adjudicated by the EAC. Intervention of heart failure decompensation is defined as an event that requires "invasive intervention (i.e. IV diuretics, ultrafiltration, or equivalent) or inpatient hospitalization".

The EAC will determine if an endpoint has been met. Sites may adhere to their standard practice diagnosing heart failure, but are required to report all diagnostic assessments, tests and procedures done with supporting material as appropriate to allow the EAC to adjudicate.

The analysis will use time to event in study for each subject, defined from the date of randomization (per randomization form) to date of last follow-up or date of primary event, whichever is first. The date of the event will be the date of death or the date of initiation of treatment for heart failure decompensation as determined by the EAC. Subjects without

primary event will be followed up until study closure. Subject deaths and HF events will be collected on case report forms. Any events that occur before the date of randomization will not be included in the intent-to-treat analysis. If a subject has more than one event that contributes to the primary endpoint, the first of these events will be used in the test statistic.

The study will be event driven, based on the number of patients that experienced an event. The study will continue until a predetermined number of events have been observed, unless the DMC advises to stop earlier.

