4.3.4 Sensitivity Analyses: LBBB Determination and aCRT Programming

As indicated in section **Error! Reference source not found.**, two sensitivity analyses will be performed for the primary objective. One is an ITT analysis of the randomized patients whose LBBB is confirmed by the ECG Core Lab. The purpose of this sensitivity analysis is to verify the effect of aCRT on the incidence of HF events or death among the true LBBB patients and to assess the impact of LBBB misclassification on the results. This analysis will be conducted in a similar way to that of the primary analysis:

```
PROC PHREG DATA=LBBB;  
CLASS NYHA site;  
MODEL time*event(0) = rand / TIES=efron;  
STRATA NYHA;  
RANDOM site/ dist = gamma;  
RUN;
```

Here, 'event', 'time' and 'aCRT' are defined in the same way as those in the primary analysis. A p-value for treatment below the cumulative α -level of approximately 0.00002, 0.00304, 0.0193 and 0.05 at the 1st, 2nd, 3rd interim and the final analysis, respectively, is significant.

The other sensitivity analysis will also be conducted in the randomized patients with ECG Core Lab confirmed LBBB, while the purpose is to verify the effect of aCRT on the primary endpoint based on the actual aCRT programming over time. Given this being said, this analysis will not follow the ITT principle and:

- Patients with major eligibility violations will be excluded (also when the violation becomes apparent only after randomization).
- Patients with major protocol violations after randomization, such as being programmed permanently to a mode that deviated from original randomization assignment due to a system modification after randomization, will be censored at the time of protocol violations.
- Patients' actual aCRT programming will be a time-varying covariate that has 3 categories: ACRT ON, ACRT OFF, and Neither, counting from the time randomization programming is implemented.

This analysis will be conducted using the following SAS PHREG procedure:

```
PROC PHREG DATA=LBBBCross COVSANDWICH (AGGREGATE) ;  
  ID pt;  
  CLASS NYHA site pt;  
  MODEL (start,stop)*event(0) = aCRTprog / TIES=efron;  
  STRATA NYHA;  
RUN;
```

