where aCRTprog indicates patients' actual aCRT programming. Patients whose actual aCRT programming change over time get multiple records in the input dataset. Whenever there is a change, for instance, there will be one record in the randomized arm up until time of crossover and another record from time of crossover until the time that a primary endpoint is met or the time of censoring without meeting a primary endpoint. The COVSANDWICH option ensures the model accounts for multiple records coming from the same patient. In order to implement the COVSANDWICH option in SAS, random site effect will not be considered in this sensitivity analysis. A p-value for treatment below the cumulative α -level of approximately 0.00002, 0.00304, 0.0193 and 0.05 at the 1st, 2nd, 3rd interim and the final analysis, respectively, is significant.

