The first sensitivity analysis is to verify the effect of aCRT treatment on HF event among the true LBBB patients. The same model used in the primary analysis will be used in this sensitivity analysis. The only difference is that patients included in the sensitivity analysis must have their LBBB confirmed by ECG Core Lab.

```
PROC PHREG DATA=HFevent_LBBB;  
  CLASS NYHA site;  
  MODEL time*HFevent(0) = rand / TIES=efron;  
  STRATA NYHA;  
  RANDOM site/dist = gamma;  
RUN;
```

The second sensitivity analysis is to check the effect of aCRT on HF event based on the actual aCRT programming, given that patients' LBBB has been confirmed by the ECG Core Lab. Again, actual aCRT programming will be a time-varying covariate, meaning patients whose actual aCRT programming change over time will have multiple records in the input dataset. This will be performed using the COVSANDWICH option in the SAS PHREG procedure, and random site effect will not be considered in this sensitivity analysis.

```
PROC PHREG DATA=HFevent_LBBBCross COVSANDWICH (AGGREGATE);  
  ID pt;  
  CLASS NYHA site pt;  
  MODEL (start,stop)*HFevent(0) = rand / TIES=efron;  
  STRATA NYHA;  
RUN;
```

Subgroup Analysis: Interaction with Treatment

The same subgroups that are considered for the primary endpoint and 1st secondary endpoint will be considered for intervention for heart failure decompensation. These include:

- Geography: US/Canada vs. International
- Age
- Gender: Males vs. Females
- QRS duration: ≤150ms vs. >150ms
- AV conduction time: median as cutoff
- LBBB: Core Lab confirmed vs. Core Lab not confirmed

- NYHA class (in different model where NYHA class is a covariate not a stratification factor)
- HF etiology
- Renal dysfunction
- Diabetes

The effects of treatment by subgroup interaction on intervention for heart failure decompensation will be evaluated using codes similar to:

```
PROC PHREG DATA=HFevent_Subgroup;  
  CLASS NYHA site Subgroup;  
  MODEL time*HFevent(0) = rand subgroup rand*subgroup / TIES=efron;  
  STRATA NYHA;  
  RANDOM site/dist = gamma;  
RUN;
```

Ancillary Analysis: Covariate Adjustment

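### The as-treated analyses drop the site effect for a reason that does not hold; site should stay in, because actual programming is not randomised

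*SAP*

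**What the plan says.** SAP 4.3.4 sets up the as-treated analysis of the primary endpoint in patients with core-laboratory-confirmed LBBB. Actual programming is a time-varying covariate: "MODEL (start,stop)*event(0) = aCRTprog / TIES=efron". A patient who changes programming has one record up to the change and "another record from time of crossover until the time that a primary endpoint is met" or follow-up is censored.

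The section gives one purpose for the sandwich variance: "The COVSANDWICH option ensures the model accounts for multiple records coming from the same patient". It gives one reason for leaving site out: "In order to implement the COVSANDWICH option in SAS, random site effect will not be considered in this sensitivity analysis". SAP 4.4.1 (mortality) repeats the choice, "using the COVSANDWICH option in the SAS PHREG procedure, and random site effect will not be considered in this sensitivity analysis", and so does 4.4.2 (HF events): "random site effect will not be considered in this sensitivity analysis". NYHA class remains a stratum. In all three code blocks site appears in the CLASS statement but is used nowhere else.

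Elsewhere site is kept. Randomisation is stratified by center and NYHA class (protocol 11.2.2). The primary model carries a gamma site frailty (SAP 4.3.2), and so does the LBBB-confirmed intention-to-treat sensitivity analysis (SAP 4.3.4). SAP 4.3.7 states that the intention-to-treat principle does not apply to the analysis by actual programming.

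**The concern.** The SAP treats the sandwich variance and the site effect as alternatives and keeps the sandwich. If the sandwich is not needed for its stated purpose, site adjustment is lost for nothing.

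It is lost where it is most useful. Between randomised arms, site is balanced by the stratified allocation. Between programming states it need not be, because reprogramming is decided during follow-up at the center. If centers differ both in patient risk and in how often they cross patients over, the comparison of ON time with OFF time is partly a comparison of centers.

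The result will be read. SAP 4.3.4 calls a p-value below the interim or final alpha level significant for this analysis. SAP Table 2 sends the primary-objective sensitivity analyses to the DMC and to the final report. The natural comparison is with the LBBB-confirmed intention-to-treat analysis, which keeps the frailty, so exposure and model change at the same time.

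**Working it through.** **1. Does splitting records matter?**

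The Cox partial likelihood is the product, over event times t, of exp(βx of the failing patient) divided by the sum of exp(βx) over all records with start < t ≤ stop. If a patient's follow-up (0, Y] is cut at c into (0, c] and (c, Y], exactly one piece covers any t. The patient is in each risk set once. The patient also has at most one event: for the primary endpoint "the first of these events will be used in the test statistic", death occurs once, and the HF-event analysis uses the first event. Numerator, denominator, score and information are therefore unchanged.

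Numerical checks on simulated data agree:

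- Randomised arm as covariate: one record per patient gives log HR −0.037879, SE 0.065172. Split records give the same values; the patient-clustered sandwich SE is 0.065167.
- Actual programming as covariate: log HR −0.091717, SE 0.065187. Cutting every record again at random points leaves both unchanged; the sandwich SE is 0.064901.
- Across all scenarios below, mean model SE and mean sandwich SE differ by at most 0.0002.

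Clustering by patient is needed in the recurrent HF-event model of SAP 4.4.2, where one patient can contribute several events. It is not needed here.

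**2. What can omitting site do?**

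The plan gives no figure for this, so it was simulated on the protocol version 2.0 design (section 11.3.4). The event model reproduces that design. The control hazard is −ln(0.85)/2 = 0.0813 per year. With HR 0.81818, 4 years of accrual and 3.5 more years of follow-up, the event probabilities are 0.358 and 0.304 (mean 0.331), and 1100/0.331 gives about 3324 patients against 3326 stated.

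Inputs from the documents: 3500 × 0.90 = 3150 confirmed-LBBB patients, 250 sites, crossover 5% (ON) and 8% (OFF) at 2 years, loss 5% at 2 years. Assumptions: true HR of actual programming 0.82, gamma site variance 0.1 to 0.5, and the link between crossover and site risk (log-linear; coefficient 0.8 on a site risk score in the clustered rows, stronger in the last row). NYHA strata were left out. There were 400 replicates per row; Monte Carlo error is about 0.003 on the log HR.

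| Crossover pattern | Site variance | No site | Gamma frailty | Stratified by site |
|---|---|---|---|---|
| Unrelated to site | 0.1 | 0.819 | 0.817 | 0.818 |
| Unrelated to site | 0.25 | 0.828 | 0.822 | 0.822 |
| OFF-to-ON commoner at high-risk sites | 0.1 | 0.858 | 0.845 | 0.823 |
| OFF-to-ON commoner at high-risk sites | 0.25 | 0.876 | 0.843 | 0.821 |
| Opposing patterns in the two arms | 0.25 | 0.910 | 0.855 | 0.815 |
| Opposing patterns, stronger | 0.5 | 0.969 | 0.862 | 0.819 |

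Share of the log HR lost in rows 3 and 4, as 1 − ln(estimate)/ln(0.82):

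- No site: 1 − 0.153/0.198 = 23% and 1 − 0.132/0.198 = 33%.
- Gamma frailty: 1 − 0.168/0.198 = 15% and 1 − 0.171/0.198 = 14%.

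The small shift in row 2 is not confounding. It is the usual attenuation when a frailty is omitted.

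Two other runs show how far the size depends on the assumptions. One gave 0.821 to 0.826 without site when crossover was unrelated to site, and 0.854 to 0.882 when it was clustered (truth 0.82). A milder link (truth 0.80, crossover 3 or 6 times as frequent in the highest-risk fifth of sites, site variance 0.3 to 0.5) gave 0.814 to 0.829 without site and 0.800 to 0.806 with the frailty.

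**3. Cost of stratifying by site**

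In rows 3 and 4 the SE rises from 0.0647 to 0.0676 and from 0.0655 to 0.0685, about 5% each, with site as the only stratum. A separate run gave about 12%. The cost grows as strata thin out: 3150/250 = 12.6 patients per site, or about 4 per cell when site is crossed with three NYHA classes.

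**4. Text against code**

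SAP 4.4.1 says actual programming is the covariate, but its code reads "MODEL (start,stop)*death(0) = rand / TIES=efron". The 4.4.2 code does the same for HF events. SAP 4.3.2 defines `rand` as the randomised group. Run as printed, these two analyses compare randomised arms; only the 4.3.4 code models programming.

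**The case against.** Several points on the other side stand.

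- The sandwich does no harm, and it can be defended as protection against a misspecified model. That is not the reason the SAP gives, though, and it does not require losing site: a stratified Cox model can carry a sandwich variance.
- The protocol works against center-driven crossover. Section 5.5 requires Steering Committee approval for reprogramming except in clinical or technical urgency, and failure to obtain it is a deviation. The planning crossover rates are only 5% and 8% at 2 years. This makes a strong link with site less likely but does not exclude one.
- The choice is prespecified and confined to sensitivity analyses.
- The simulations leave out the SAP's exclusions for eligibility violations and its censoring of some permanent programming deviations.

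A reader might infer that all three as-treated hazard ratios are confounded by site. The documents do not support that. They give no between-site variance and no link between crossover and site risk. For mortality and HF events, the concern applies to the text and not to the code as printed.

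A reader might also infer that restoring the frailty makes the as-treated result an estimate of the effect of programming. It does not. A frailty assumes site effects independent of exposure, which is the assumption that site confounding breaks. No site term removes patient-level confounding such as crossover for worsening heart failure, which the protocol anticipates in its Clinical Composite Score definition (section 11.5.1).

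**Conclusion.** The stated reason for dropping site does not hold. This follows from the record structure and needs no assumption. The consequence is a possible bias, not a demonstrated one: it requires centers to differ both in risk and in crossover. The shift is under 0.01 on the hazard ratio if crossover is unrelated to site. It is from 0.82 to about 0.85 to 0.88 if OFF-to-ON crossover clusters at high-risk sites as assumed, less under the milder link and more under the extreme patterns. Direction also depends on the pattern: clustering at low-risk sites would push the estimate away from the null.

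The primary intention-to-treat analysis is untouched. This is a cheap improvement to supporting analyses and does not threaten the trial's conclusion.

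**What to change.** In SAP 4.3.4, 4.4.1 and 4.4.2, delete the sentences that drop the site effect, and name in advance one of these for the as-treated models:

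- **Stratify by site:** `STRATA NYHA site;`. This needs no RANDOM statement, so the SAS conflict named in 4.3.4 does not arise, and COVSANDWICH(AGGREGATE) may stay. It removed nearly all of the simulated site confounding. If strata become too thin, the small-site pooling rule in SAP 4.1.2.4 can be applied.
- **Gamma site frailty on the (start, stop) data, without COVSANDWICH:** this matches the LBBB-confirmed intention-to-treat model, so the two results differ in exposure and not in model form, but it removes only part of any site confounding. In the R survival library already used in SAP 4.4.2: `coxph(Surv(start, stop, event) ~ aCRTprog + strata(NYHA) + frailty(site, distribution='gamma'))`.

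Stratification is the better choice if the aim is protection against site confounding; the frailty fit can be shown beside it for comparability.

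In the as-treated code of 4.4.1 and 4.4.2, replace `rand` with the actual-programming covariate. Add one sentence saying that site adjustment does not address patient-level reasons for crossover.

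The cost is SAP wording and a few lines of code in three sensitivity analyses, with no new data. Stratifying also costs some precision: about 5% to 12% on the SE in the simulations, and more if site-by-NYHA cells are very small.
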